4.5.2 Other Safety Variables

Other safety variables are listed below:

- OST examination
- OHT examination

4.5.2.1 OST Examination

Where possible, this procedure should be conducted by a single dental examiner or clinically qualified designee. The OST examination will be accomplished throughout the study by direct observation and palpation with retraction aids as appropriate. The examiner will include examination of the labial mucosa (including lips), buccal mucosa, mucogingival folds, gingival mucosa, hard palate, soft palate, tonsillar area, pharyngeal area, tongue, sublingual area, submandibular area, and salivary glands.

The results of the examination will be recorded in the CRF as either normal or abnormal, with details of any abnormalities. Any post-treatment soft tissue abnormality, or worsening of a preexisting condition, observed by the examiner, or reported by the subject will be recorded on the CRF. Any abnormalities or worsening of a preexisting condition observed by the clinical examiner or reported by the subject from the OST examination carried out at Screening will be recorded as an AE.

OST will be summarized (number of subjects and percentages with abnormalities, without abnormalities, or OST not examined) by visit and study product in Table 14.3.4.1 for all subjects in the Safety Population. OST examination will be listed (Listing 16.2.8.1) for all randomized subjects.

4.5.2.2 OHT Examination

Where possible, this procedure should be conducted by a single dental examiner or clinically qualified designee for all subjects.

The OHT examination will assess grossly carious lesions or signs of erosive wear, enamel irregularities, tooth fracture, gross decay, decalcification, faulty restorations, and implants. The examination will be performed by direct observation.

Observations will be listed as absent or present, and conditions noted as present will be described. Examination findings will be described and documented in the CRF. Any abnormalities or worsening of a pre-existing condition observed by the clinical examiner or reported by the subject from the OHT examination carried out at Screening will be recorded as an AE.

OHT examination will be listed (Listing 16.2.8.2) for all randomized subjects.

4.6 Analysis of Other Variables

4.6.1 Repeatability of the Examiner

Repeat MGI and TPI assessments will be performed by the clinical examiner at Day 0 (Visit 2; Baseline), Week 3 (Visit 3), Week 6 (Visit 4) and Week 12 (Visit 5). At least 1 repeat assessment should be performed for each index on each clinical assessment day, that is, at least one MGI and one TPI repeat assessment on each assessment day. ‘Repeat’ subjects will be

selected at random from those in attendance. Different subjects can be used for repeat MGI and TPI assessments. In the event that the same subject is selected at random for repeatability assessments at multiple visits, the pairs of observations will be considered as independent for the purposes of repeatability analysis; that is, any potential with-subject correlation will be ignored.

There should be a delay of at least 10 minutes between original and repeat assessments for a given subject and ideally separated by another subject. No other procedure on the subject should be carried out between the first and the repeat assessment.

Scores from the first assessment must not be visible to the examiner/scribe when the repeat assessment is carried out.

The repeat MGI and TPI assessments will be compared to the respective original assessments (inclusive of any tooth surfaces assessed as missing or not qualified). The repeat assessments will not be used in any efficacy analysis.

The first and second assessments of each index will be analyzed with a Fleiss-Cohen weighted kappa coefficient (κ), along with the 95% CI, to assess the intra-examiner reliability. Reliability will be deemed:

- Excellent if $\kappa > 0.75$
- Fair to good if $0.4 \leq \kappa \leq 0.75$
- Poor if $\kappa < 0.4$

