#### AT SCREENING (Visit 1):

- a. Subject with at least 20 natural, permanent teeth.
- b. Subject with at least 40 evaluable surfaces for MGI, BI, and TPI.

*An evaluable surface is defined as having 2/3rds of the natural tooth surface gradable for the selected clinical indices. The following should not be included in the evaluable surface count- third molars; fully crowned/extensively restored, grossly carious, orthodontically banded/bonded or abutment teeth; surfaces with calculus deposits which, in the opinion of the clinical examiner, would interfere with the baseline assessments of the selected clinical indices.*

- c. A subject with plaque-induced gingivitis, in the opinion of the clinical examiner, as confirmed by a gross visual examination at the Screening Visit.

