4.4.2.3 Change from Baseline in Modified Gingival Index (MGI)

The MGI will be assessed on the facial and lingual surfaces of each scorable tooth (7-7 in each arch). Two scores (according to the scale in [Table 4-2](#) below) should be recorded buccally/labially (papilla and margin) and two scores lingually/palatally (papilla and margin). At each visit, each subject therefore has up to 112 evaluable tooth sites (i.e. 4 measurements on up to 28 scorable teeth).

Table 4-2 Modified Gingival Index Scoring System

Score Description	
0	Absence of inflammation
1	Mild inflammation; slight change in colour, little change in colour; little change in texture of any portion of the marginal or papillary gingival unit
2	Mild inflammation; criteria as above but involving the entire marginal or papillary gingival unit
3	Moderate inflammation; glazing, redness, edema, and/ or hypertrophy of the marginal or papillary gingival unit
4	Severe inflammation; marked redness, edema and/ or hypertrophy of the marginal or papillary gingival unit, spontaneous bleeding, congestion, or ulceration
9	Missing tooth or not qualified tooth

The MGI score for each subject at each visit is calculated as the sum of index values over all evaluable tooth sites, divided by the number of evaluable tooth sites. Evaluable tooth sites are those scored as 0, 1, 2, 3 or 4 so the MGI score has a range of 0 to 4.

Descriptive statistics (n, mean, SD, SE, median, minimum, and maximum) will be presented for the MGI score at each time point (absolute value, change from baseline and percent change from baseline) in [Table 14.2.4.1.1](#). Raw means (\pm SE) of the MGI score at each time point will be plotted by study product in [Figure 14.2.4.1.3](#) for all subjects in the mITT population.

Additionally, the number and percentage of subjects whose MGI score has reduced (improved), remained the same and increased (worsened), respectively compared to baseline, will be presented by study product at each time point in [Table 14.2.4.1.2](#) for the mITT population.

Individual data for the MGI assessment at each evaluable tooth site will be listed for each subject in [Listing 16.2.6.3.1](#), and individual data for the derived MGI score will be listed for each subject in [Listing 16.2.6.3.2](#), by study product group and visit for all randomized subjects.

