4.4.2.4 Change from Baseline in Turesky Plaque Index (TPI)

The TPI will be used to assess plaque on all gradable teeth meeting the inclusion/exclusion criteria (natural teeth only). The TPI will be assessed on the facial and lingual surfaces of each scorable tooth (7-7 in each arch). Three scores (according to the scale in [Table 4-3](#) below) should be recorded buccally/labially (distal, body and mesial sites) and three scores lingually/palatally (distal, body and mesial sites). At each visit, each subject therefore has up to 168 evaluable tooth sites (i.e. 6 measurements on up to 28 scorable teeth).

Table 4-3 Turesky Plaque Index Scoring System

Score Description	
0	No plaque
1	Separate flecks of plaque at the cervical margin
2	Thin continuous band of plaque (up to 1 mm) at the cervical margin
3	Band of plaque wider than 1 mm but covering < 1/3 of the tooth surface
4	Plaque covering ≥ 1/3 but < 2/3 of the tooth surface
5	Plaque covering ≥ 2/3 of the tooth surface

Score Description

9 Missing tooth or not qualified tooth

The overall TPI score for each subject at each visit is calculated as the sum of index values over all evaluable tooth sites, divided by the number of evaluable tooth sites. Evaluable tooth sites are those scored as 0, 1, 2, 3, 4 or 5 so the overall TPI score has a range of 0 to 5.

The interproximal TPI score for each subject at each visit is calculated as the sum of index values over all evaluable distal and mesial tooth sites, divided by the number of evaluable distal and mesial tooth sites. Similar to the overall TPI score, the interproximal TPI score has a range of 0 to 5.

Descriptive statistics (n, mean, SD, SE, median, minimum, and maximum) will be presented at each time point (absolute value, change from baseline and percent change from baseline) in Table 14.2.5.1.1 for overall TPI score and in Table 14.2.5.1.3 for interproximal TPI score. Raw means (\pm SE) at each time point will be plotted by study product in Figure 14.2.5.1.5 for overall TPI score and in Figure 14.2.5.1.6 for interproximal TPI score, for the mITT population.

Additionally, the number and percentage of subjects whose score has reduced (improved), remained the same and increased (worsened), respectively compared to baseline, will be presented by study product at each time point in Table 14.2.5.1.2 (overall TPI score) and Table 14.2.5.1.4 (interproximal TPI score) for the mITT population.

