4.6.1.1 MGI Repeatability

The first and repeat values of the MGI for each tooth site will be combined and cross-tabulated for the MGI Repeatability population (Table 14.2.6.1). Only subjects with both first and repeat MGI assessments available for a given tooth site at the same visit will be presented and analyzed.

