4.6.1.2 TPI Repeatability

The first and repeat values of the TPI for each tooth site will be combined and cross-tabulated for the TPI Repeatability population (Table 14.2.6.2). Only subjects with both first and repeat TPI assessments available for a given tooth site at the same visit will be presented and analyzed.

5 Changes to the Protocol Defined Statistical Analysis Plan

Changes from the originally planned statistical analysis specified in the protocol are outlined in Table 5-1 below.

Table 5-1 Changes to Protocol Defined Statistical Analysis Plan

Protocol	Statistical Analysis Plan	
Statistical Analysis Section	Statistical Analysis Plan	Rationale for Changes
No mention of a suitable non-parametric test of the primary efficacy endpoint.	Section 4.4.1.2: The assumption of normality and homogeneity of variance in the MMRM will be investigated. In case of violation of these assumptions, a Wilcoxon Signed Rank Test (within product comparisons with baseline) will be performed to support the MMRM results.	For consistency with previous studies, where Wilcoxon Signed Rank p-values were added for inclusion in the Clinical Study Report.
No mention of a suitable non-parametric test of within-group comparisons to baseline for the secondary efficacy endpoints.	Sections 4.4.2.1.1, 4.4.2.2.1, 4.4.2.3.1 and 4.4.2.4.1: The assumption of normality and homogeneity of variance in the MMRM will be investigated. In case of violation of these assumptions, a Wilcoxon Rank Sum test (between products comparisons) and Wilcoxon Signed Rank Test (within product comparisons with baseline) will be performed to support the MMRM results.	For consistency with previous studies, where Wilcoxon Signed Rank p-values were added for inclusion in the Clinical Study Report.

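### The 95% CI for the examiner's weighted kappa makes no allowance for clustering of tooth sites within subjects, so it is too narrow if agreement is correlated within a mouth

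*SAP*

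**What the plan says.** SAP 4.6.1 (Repeatability of the Examiner) compares first and repeat scores with a Fleiss-Cohen weighted kappa, "along with the 95% CI, to assess the intra-examiner reliability". Protocol 12.3.4 specifies the same statistic and interval. Neither names a variance method.

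The unit of analysis is the tooth site. SAP 4.6.1.1 says "The first and repeat values of the MGI for each tooth site will be combined and cross-tabulated", and SAP 4.6.1.2 says "The first and repeat values of the TPI for each tooth site will be combined and cross-tabulated". Each table covers the whole repeatability population, which SAP 4.1.3 defines as anyone with a repeat at any visit.

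For a subject selected at more than one visit, SAP 4.6.1 says that "the pairs of observations will be considered as independent for the purposes of repeatability analysis; that is, any potential with-subject correlation will be ignored".

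Each mouth supplies many sites. For MGI, "each subject therefore has up to 112 evaluable tooth sites" (SAP 4.4.2.3). For TPI, "each subject therefore has up to 168 evaluable tooth sites" (SAP 4.4.2.4).

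**The concern.** Two kinds of dependence are left out of the interval.

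- **Stated.** Pairs from one subject at different visits are treated as independent.
- **Inferred.** Sites within one mouth at one examination are also treated as independent. The plan does not say this, but it follows from pooling by site with no clustered variance, subject-level resampling or per-subject kappa.

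The inferred part is probably the larger. Every repeat examination brings in a full mouth of sites, whether or not that subject is drawn again. How often subjects will be drawn twice cannot be read from the documents.

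Sites scored in one sitting share the subject, the session and the examiner's state at the time, so positive correlation of agreement is plausible. If it is present, the effective sample size is well below the number of sites and the standard interval is too short.

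What is at stake is how precisely examiner repeatability is reported. A single examiner scores every subject and BI has no repeat assessments, so these two kappas are the only repeatability evidence the study will produce.

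**Working it through.** **Inputs from the documents**

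- MGI sites per mouth: 4 scores × 28 teeth = 112, as the SAP states.
- TPI sites per mouth: 6 scores × 28 teeth = 168, as the SAP states.
- Lower end: protocol 5.2 requires "Subject with at least 20 natural, permanent teeth". With all 20 scorable, that is 4 × 20 = 80 MGI sites and 6 × 20 = 120 TPI sites.

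**Not in the documents, so assumed**

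- The ICC of agreement within a mouth: taken as 0, 0.01 and 0.05.
- The number of repeat examinations. The plan asks for at least one per index per assessment day and gives no total. The ratios below do not depend on it; the absolute widths do.

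The plan gives no expected kappa, standard error or interval width, so it has no figure of its own to reproduce beyond the site counts.

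**Design effect**

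With m sites per mouth, the ratio of the true SE to the independent-sites SE is √(1 + (m − 1) × ICC). The coverage of a nominal 95% interval built on the smaller SE is 2Φ(1.96 / ratio) − 1.

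Example for MGI with m = 112 and ICC 0.01: √(1 + 111 × 0.01) = √2.11 = 1.45, and coverage is 2Φ(1.96 / 1.45) − 1 = 0.82.

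Example for TPI with m = 168 and ICC 0.05: √(1 + 167 × 0.05) = √9.35 = 3.06, and coverage is 2Φ(1.96 / 3.06) − 1 = 0.48.

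Each cell gives the SE ratio (the factor by which the CI should widen), with coverage in brackets.

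| Sites per mouth | ICC 0 | ICC 0.01 | ICC 0.05 |
|---|---|---|---|
| MGI, 112 | 1.00 (95%) | 1.45 (82%) | 2.56 (56%) |
| TPI, 168 | 1.00 (95%) | 1.63 (77%) | 3.06 (48%) |
| MGI, 80 | 1.00 (95%) | 1.34 (86%) | 2.22 (62%) |
| TPI, 120 | 1.00 (95%) | 1.48 (81%) | 2.64 (54%) |

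These are cluster sizes per examination. A subject drawn at two visits forms a larger cluster, which the table does not include.

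**Simulation check**

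The design effect is an approximation for kappa, so it was checked by simulating the quadratic-weighted kappa directly, with 600 datasets per setting.

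1. *Examiner error SD differing between subjects (log-SD 0.15 or 0.30), 15 or 30 repeat subjects, kappa 0.66–0.69.* For 112 sites the SE ratio was 1.5 and 2.2–2.3, with coverage 81% and 59%. For 168 sites it was 1.9 and 2.9–3.0, with coverage 70–72% and 48–50%. Inverting the formula, ICC = (ratio² − 1) / (m − 1), the milder setting corresponds to about 0.01–0.02 and the harsher to about 0.035–0.05. A delete-one-subject jackknife with t quantiles covered 93–96%.
2. *Mouth-level variation in severity, in shared examiner error, or in both, with 20, 40 or 80 repeat examinations.* With neither present, the independent-sites interval covered 94–96%. With variation present it covered 72–90% (MGI) and 65–88% (TPI). A mouth-clustered SE covered about 92–96%. Mean kappa stayed at 0.685–0.692 throughout, so the estimate is not disturbed. Severity differences alone, with no shared examiner error, gave ratios of about 1.25–1.5.

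**Absolute size**

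This is the setting in the second simulation with the most mouth-level variation, at 40 examinations.

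| Index | Independent-sites SE | True SE | 95% half-width, independent | 95% half-width, true |
|---|---|---|---|---|
| MGI | 0.0078 | 0.0138 | 1.96 × 0.0078 = 0.015 | 1.96 × 0.0138 = 0.027 |
| TPI | 0.0063 | 0.0126 | 1.96 × 0.0063 = 0.012 | 1.96 × 0.0126 = 0.025 |

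**The case against.** The strongest reply is that nothing turns on this interval. The excellent, fair-to-good and poor bands are set on kappa itself. Repeat scores are barred from efficacy analyses. The primary endpoint and the one confirmatory secondary comparison come from BI, which has no repeatability exercise. This stands, and it is why the point is minor.

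Second, the between-visit assumption is openly disclosed. That is true, but disclosure does not restore coverage, and the within-mouth part is not mentioned at all.

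Third, the size depends on outside assumptions, and low coverage percentages sound worse than errors of hundredths of kappa. This also stands. Even with 15 subjects and the harsher examiner-error setting, the true half-width for MGI was about 0.06 (SE about 0.030 against 0.014), while the fair-to-good band is 0.75 − 0.40 = 0.35 wide. The interval would mislead mainly near a cut-off.

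Fourth, SAP 4.6.1 keeps sites marked missing or not qualified (code 9) in the comparison. Read literally, a 20-tooth subject would still supply 112 or 168 pairs, and the 80- and 120-site rows would not apply. In a trial calculation with about two missing teeth per mouth and 9 scored as a number, kappa rose from about 0.69 to 0.92. The SE ratio stayed near 2.1–2.3, so the clustering point survives, although the absolute widths roughly halve. How code 9 enters the table is a separate question.

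**Conclusion.** The concern holds. Followed as written, the plan gives a kappa interval that is too narrow under positive within-mouth correlation of agreement. At full dentition it should be about 1.5 to 2.6 times as wide for MGI and 1.6 to 3.1 times for TPI, over an assumed ICC of 0.01 to 0.05. At ICC 0 there is no error.

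Confidence is high that clustering is not accounted for: it is stated for repeat visits and inferred for sites within a mouth. Confidence is low on the size, because neither the ICC nor the number of repeat examinations is in the documents. The consequence is limited to the reported precision of examiner repeatability.

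**What to change.** Keep the pooled weighted kappa as the estimate. In SAP 4.6.1, replace the sentence that ignores within-subject correlation with a rule that the 95% CI uses the subject as the cluster, with all of a subject's sites and visits kept together. A jackknife, a bootstrap over subjects or a cluster-robust variance would each serve, but the SAP should name one. A delete-one-subject jackknife with t quantiles is a reasonable default, given its 93–96% coverage in the check. Report the number of subjects and repeat examinations beside each kappa.

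The cost is a few lines of SAS and no new data. The interval will usually be wider, and with few repeat subjects it remains approximate. The handling of code 9 sites needs its own decision.

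### The MGI and TPI examiner kappa counts sites coded 9 (missing or not qualified), so it does not measure grading reliability alone and can be too high or too low

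*SAP*

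**What the plan says.** SAP 4.6.1 (Repeatability of the Examiner) sets out the comparison of first and repeat reads. The repeat scores are "compared to the respective original assessments (inclusive of any tooth surfaces assessed as missing or not qualified". The two reads are then analysed with a Fleiss-Cohen weighted kappa and its 95% CI, and the result is labelled *Excellent* above 0.75, *Fair to good* from 0.4 to 0.75, and *Poor* below 0.4.

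SAP Table 4-2 gives code 9 to a "Missing tooth or not qualified tooth", and Table 4-3 does the same for TPI. Neither scale treats 9 as a grade. For MGI, "Evaluable tooth sites are those scored as 0, 1, 2, 3 or 4"; for TPI, "Evaluable tooth sites are those scored as 0, 1, 2, 3, 4 or 5".

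SAP 4.6.1.1 adds a table: "The first and repeat values of the MGI for each tooth site will be combined and cross-tabulated for the MGI Repeatability population". It then limits the analysis: "Only subjects with both first and repeat MGI assessments available for a given tooth site at the same visit will be presented and analyzed". SAP 4.6.1.2 does the same for TPI. Neither subsection says whether a recorded 9 counts as available.

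Protocol 12.3.4 plans the same kappa without mentioning missing or unqualified sites, and SAP Table 5-1 does not list their inclusion as a change.

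**The concern.** Quadratic weights penalise a disagreement by the squared distance between the two scores. That has meaning between grades but not between a grade and a status code. The SAP does not say whether 9 enters at its face value or as the rank after the top grade, and the two choices give different kappas.

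The distortion runs in two directions:

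- **9 at both reads**, as a missing tooth should be. The pair adds no observed disagreement, while the distant score raises the disagreement expected by chance. Kappa rises without any better grading.
- **9 at one read only.** The pair adds a large squared penalty. Kappa can fall below its value on graded sites.

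Both can occur. Protocol 5.2 asks for at least 20 natural teeth against 28 scorable positions, so 8/28 = 28.6% of positions can be empty in an eligible subject. Other exclusions rest on judgement, such as "surfaces with calculus deposits which, in the opinion of the clinical examiner, would interfere with the baseline assessments" in Protocol 5.2, or whether a filling prevents accurate TPI grading (Protocol 9.2.4).

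Agreement on whether a site can be graded is a legitimate part of repeatability. One weighted kappa cannot separate it from agreement on the grade, and the fixed cut-offs are then applied to the mixture.

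**Working it through.** The documents state no kappa value, so there is no planned figure to reproduce. The check asks how far inclusion of code 9 moves kappa from its value on graded sites.

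**Inputs from the documents.** Code 9 and the grade ranges 0-4 and 0-5 (SAP Tables 4-2 and 4-3); 28 scorable teeth (SAP 4.4.2.3 and 4.4.2.4); quadratic weights and cut-offs 0.4 and 0.75 (SAP 4.6.1).

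**Assumptions, not in the documents.** MGI mean 2.0, SD 0.70-1.20; TPI mean 2.5, SD 0.90-1.43. Code 9 is scored as 9 (numeric) or as the next rank (5 for MGI, 6 for TPI). One or two teeth in 28 are coded 9.

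**Formula.** Let k be kappa on graded sites, m and v the mean and variance of the grades, S the score given to code 9, D = (S - m)², p the share of sites coded 9 at each read, and d the share of those 9s that are graded at the other read. Then kappa = 1 - Do/De, with

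- Do = (1 - p - pd)·2v(1 - k) + 2pd·(v + D)
- De = 2(1 - p)(v + pD)

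**All 9s concordant (d = 0).** This reduces to kappa = 1 - (1 - k)·v/(v + pD). With one tooth, p = 1/28. The extremes for k = 0.30 are:

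| Case | v | pD | Kappa |
|---|---|---|---|
| MGI, SD 0.70, numeric | 0.49 | 49/28 = 1.75 | 1 - 0.7 × 0.49/2.24 = 0.85 |
| TPI, SD 1.43, numeric | 2.045 | 42.25/28 = 1.509 | 1 - 0.7 × 2.045/3.554 = 0.60 |
| MGI, SD 0.70, rank | 0.49 | 9/28 = 0.321 | 1 - 0.7 × 0.49/0.811 = 0.58 |
| TPI, SD 1.43, rank | 2.045 | 12.25/28 = 0.4375 | 1 - 0.7 × 2.045/2.482 = 0.42 |

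So 0.30 becomes 0.60-0.85 or 0.42-0.58, out of *Poor* either way. For k = 0.60 the same steps give 0.77-0.91 (numeric, *Excellent*) or 0.67-0.76 (rank, label mostly unchanged).

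**One tooth, 20% of its 9s discordant.** For k = 0.30, kappa is 0.51-0.68 (numeric) or 0.385-0.49 (rank), so the label can stay *Poor*.

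**Two teeth (p = 2/28), 30% discordant, k = 0.80.** Here pd = 0.0214.

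- MGI, SD 0.70, numeric: Do/2 = 0.907 × 0.49 × 0.2 + 0.0214 × 49.49 = 0.089 + 1.060 = 1.149; De/2 = 0.9286 × (0.49 + 3.5) = 3.705; kappa = 0.69.
- TPI, SD 1.43, rank: Do/2 = 0.371 + 0.306 = 0.677; De/2 = 2.711; kappa = 0.75.

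The full ranges are 0.69-0.72 (numeric) and 0.72-0.75 (rank), out of *Excellent* or at its edge. For k = 0.90 they are 0.70-0.76 and 0.76-0.82. With 20% discordant, 0.80 is nearly unchanged (0.79) and 0.90 becomes 0.80-0.86.

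**Break-even.** Setting kappa = k gives d = (1 - k)(1 - p)D/(D + kv). Over the assumed ranges and one or two teeth:

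| Graded-site kappa | Discordant share of 9s at which inclusion turns from inflating to deflating |
|---|---|
| 0.30 | 62%-67% |
| 0.60 | 34%-38% |
| 0.80 | 16%-19% |
| 0.90 | 8%-10% |

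**Sensitivity to the means.** Moving them by 0.5 either way gives 0.57-0.86 (numeric) or 0.39-0.63 (rank) for k = 0.30 with one concordant tooth, and 0.69-0.76 for k = 0.80 with two teeth and 30% discordant.

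**Two further checks.** Simulation with 1,000,000 graded site pairs agreed with the closed form to within 0.001 in the cases compared. A separate calculation with explicit grade distributions (MGI 10/35/40/14/1% over 0-4; TPI 3/12/35/35/12/3% over 0-5) gave the same directions: with 5% of sites coded 9 at both reads and scored 9, 0.30 becomes 0.85 for MGI and 0.76 for TPI.

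**The case against.** **The text may already exclude 9s.** SAP 4.6.1.1 and 4.6.1.2 admit only sites with both assessments available, and the kappa sentence does not repeat the parenthesis. But neither subsection says that a recorded 9 is unavailable, and the parenthesis in 4.6.1 explicitly includes these sites. What stands is that the passages need to be aligned.

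**The downward case is strained.** The same examiner repeats the read at the same visit with no procedure in between, and code 9 is mostly a stable property of the tooth. Two teeth with 30% discordance means 2 × (2/28) × 0.3 = 4.3% of site pairs coded 9 once, about 5 of 112 MGI or 7 of 168 TPI sites, alongside very consistent grading. The calculus wording in Protocol 5.2 governs eligibility counts rather than repeat scoring, and the fillings rule in 9.2.4 is for TPI only. This stands as to likelihood: upward is the more probable direction. It does not remove the downward mechanism.

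**The label probably holds for a good examiner.** Protocol 9.2.5 requires prior demonstrated repeatability, and 5.8 requires recent trial use of these measures. At a graded-site kappa of 0.80, one or two wholly concordant teeth give 0.84-0.98, and 10% discordance gives 0.82-0.88, all *Excellent*. This is fair. But the statistic exists to test that reliability in this trial, and the kappa and its interval would be distorted even where the label is not.

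**Nothing depends on it.** Repeat data enter no efficacy analysis, no action follows from the label, BI (the source of the primary endpoint) has no repeat exercise, and the cross-tabulation lets a reader recompute kappa. All of this stands and sets the severity.

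**Conclusion.** The concern holds and is minor. As written, SAP 4.6.1 puts a non-grade into a quadratic-weight kappa, so the reported value mixes agreement on gradability with agreement on grade and can earn a label that grading alone would not.

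The directions follow from the arithmetic and do not depend on the assumptions. The sizes do: the documents give neither the share nor the concordance of 9s, nor the score spread, nor the score for code 9. The figures show sensitivity and are not a forecast. If no site is coded 9, there is no effect. The damage is confined to the descriptive statement on examiner reliability for two secondary indices.

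**What to change.** In SAP 4.6.1, replace the parenthesis with a sentence such as: *Kappa is computed only on sites scored 0-4 (MGI) or 0-5 (TPI) at both the first and the repeat assessment.*

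In 4.6.1.1 and 4.6.1.2, state that a site coded 9 at either read stays in the cross-tabulation but not in kappa. Keep the code-9 cells visible in Tables 14.2.6.1 and 14.2.6.2, and report the number of sites coded 9 at one read only as a separate measure of agreement on gradability.

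The cost is one sentence, two matching edits, one program filter and one count taken from a table already planned. No data collection or efficacy analysis changes. The reported kappa may come out lower, or higher if 9s are often discordant, and gradability is no longer inside the headline figure.
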